1 SYNOPSIS

TITLE: Rapid HCV Test and Treat to increase HCV treatment among people who use drugs (RAPID-HCV)

DESIGN: Open label multicenter, phase IV randomized trial of a test and treat strategy with peer enhancement for HCV treatment at drug treatment programs versus standard of care referral for HCV treatment.

DURATION: Participants will be on study for up to a total of 12 months after HCV treatment initiation (treatment and observation period).

SAMPLE SIZE: 124 HCV infected participants will be enrolled in the study from five drug treatment programs in four cities (Baltimore Maryland, Birmingham Alabama, San Francisco California and Toronto Canada). Up to 15 peers and 45 drug treatment program staff members (for in-depth interviews only) will be enrolled across all sites. Total enrollment up to 184 participants.

POPULATION: People who use drugs enrolled in drug treatment programs with confirmed ongoing HCV infection.

All participants ≥ 18 years of age enrolled at study drug treatment sites who have ongoing HCV infection (as determined through study testing procedures).

STUDY DRUG AND DURATION OF TREATMENT: Subjects will receive GLE/PIB fixed-dose combination (300 mg/120 mg) QD for 8 weeks.

2 INTRODUCTION

2.1 Background and Rationale

[figure not shown]
Why Is This Study Being Conducted?

Hepatitis C virus (HCV) infection is a major public health challenge and is associated with significant morbidity and mortality.¹ The World Health Organization (WHO) has called for elimination of HCV as a public health challenge by the year 2030. The WHO elimination goals include a 90% reduction in HCV incidence and a 65% reduction in HCV related mortality by 2030 relative to 2015 rates.² However, the United States is experiencing increases in HCV incidence directly attributable to injection drug use with the steepest increase in incidence since 2011.^{3,4} Although people who use drugs (PWUD) have disproportionately high rates of HCV infection, rates of HCV treatment remain low among PWUD.^{5,6} Once initiated on HCV therapies, PWUD have been demonstrated to achieve high rates of HCV cure.⁷

HCV treatment uptake among PWUD, the core of the HCV epidemic, remains low due to multiple interrelated barriers at the level of the patient, the provider, and the system.⁸⁻¹⁰ Patient-level barriers include poor knowledge related to HCV and its treatment and absence of symptoms. These issues are compounded by general barriers to health care access (e.g., not having insurance or a primary care provider), competing comorbidities, which may require more immediate attention, and factors that impede stability, such as ongoing Substance Use Disorder (SUD), unemployment, and lack of transportation.¹¹⁻¹³ In many parts of the world, the major structural barrier of medication cost has been reduced through insurance coverage for HCV treatment by payers and removal of insurance coverage restrictions related to drug use or liver disease stage. Beyond cost, additional structural barriers include insufficient HCV treatment locations. HCV care has historically been delivered in specialist settings thus segregating HCV treatment from other services that PWUD utilize including those received at opioid treatment programs (OTPs).

Drug treatment programs such as OTPs routinely provide services for PWUD, with many patients accessing care at these settings multiple times a week. The structure of care provision at OTPs including observed dosing of opioid agonist therapies, offers a unique infrastructure upon which to layer HCV treatment. In addition, simplification of HCV treatment protocols endorsed by the major guidelines including the AASLD/IDSA¹⁴ provide an opportunity to implement HCV treatment in non-traditional settings. We propose to evaluate effectiveness of an HCV test and treat strategy at OTPs, a venue with a captive audience of patients with untreated HCV infection. To support the effectiveness of this strategy, we will use a validated protocol to identify and train peers at OTP sites to support HCV treatment engagement and reinfection prevention of PWUD recruited at these sites. The interventions we propose to test will target barriers at different levels and thus impact multiple steps in the HCV care continuum from linkage to care to cure (Figure 1).

Figure 1: HCV Treatment Barriers

2.2 Clinical Hypothesis

An HCV test and treat strategy, defined as immediate offer of and access to HCV treatment after testing HCV positive enhanced by peer support, will be associated with higher rates of HCV treatment initiation and cure compared to standard of care (SOC) referral to off-site HCV treatment.

3 STUDY OBJECTIVES AND ENDPOINTS

3.1 Objectives

The study aims to assess the effectiveness of an HCV test and treat strategy with peer enhancement compared to standard of care referral.

3.2 Primary Endpoint

The primary effectiveness endpoint is:

Treatment initiation: Proportion of participants who start HCV treatment (in initial test and treat arm versus standard of care referral arm) within 12 weeks of randomization.

3.3 Secondary Endpoints

- 1) HCV treatment completion: Proportion of those initiating treatment who complete HCV treatment defined as taking more than 90% of prescribed treatment course by expected end of treatment date.
- 2) SVR 12: Proportion of participants with HCV RNA <15 IU/ml between 10 and 36 weeks after end of treatment in each randomization arm.
- 3) Time to HCV treatment initiation after randomization.

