6.2.2 Medical Complaints/Adverse Events and Serious Adverse Events

An AE is defined as any untoward medical occurrence in a subject or clinical investigation subject administered a pharmaceutical product and which does not necessarily have a causal relationship with this treatment. An AE can therefore be any unfavorable and unintended sign (including an abnormal

laboratory finding), symptom, or disease temporally associated with the use of a medicinal (investigational) product, whether or not the event is considered causally related to the use of the product.

An AE can result from use of the drug as stipulated in the protocol or labeling, as well as from accidental or intentional overdose, drug abuse, or drug withdrawal. Any worsening of a pre-existing condition or illness is considered an AE. Worsening in severity of a reported AE should be reported as a new AE. Laboratory abnormalities and changes in vital signs are considered to be AEs only if they result in discontinuation from the study, necessitate therapeutic medical intervention, meets protocol specific criteria (see Section 6.3 regarding toxicity management) and/or if the investigator considers them to be AEs.

Adverse event reporting will follow the requirements outlined below. Adverse events will also be recorded and tracked in a safety monitoring database by the investigators. Serious adverse events (SAEs) will be reported to the Institutional Review Board according to IRB guidelines and to AbbVie via the Johns Hopkins University Transplant Oncology and Infectious Diseases Clinical Research Center (TOID CRC).

All Grade 3 or higher and all SAEs related to the use of GLE/PIB in intervention arm or prescribed DAA course in SOC arm will be collected. Thus, AEs and SAEs will only be collected from the time of first DAA dose to 30 days after completion of DAA course.

All Grade 3 or higher AEs and all SAEs will be reviewed by the principal investigator as they occur in a timely manner. All AEs related or possibly related to GLE/PIB will be reported by the site to the TOID CRC within 72 hours of the site being made aware via the REDCap EDC system. All SAEs will be reported to the TOID CRC via the REDCap EDC system within 24 hours of the site being made aware. Notification of all SAEs will be made to AbbVie by the TOID CRC via email within 24 hours of entry into REDCap.

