7.3.3 Secondary outcomes

- 1) HCV treatment completion: Proportion of those initiating treatment who complete HCV treatment defined as taking more than 90% of prescribed treatment course by expected end of treatment date.
- 2) SVR 12: Proportion of participants with HCV RNA <15 IU/ml between 10 and 36 weeks after end of treatment in each randomization arm.

Analysis for secondary outcomes 1 and 2 will be logistic regression analyses.

- 3) Time to HCV treatment initiation after randomization.

For secondary outcome 3, a time to event outcome, we will perform survival (Kaplan Meier) analysis for time to HCV treatment initiation.

Analysis of adverse event data will primarily be descriptive. Adverse event data will be compared between randomization arms using Fisher's exact Test.

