APPENDIX A. SCHEDULE OF EVENTS (ALL PARTICIPANTS)

	Recruitment Screen	Day 0	Treatment Day 1	Treatment Week 4	End of Treatment -0d/+30d	Post-Treatment Week 12 -14d/+30d	Post-Treatment Week 24 -14d/+30d	Post-Treatment Week 36 -14d/+30d	Early D/C Visit
Eligibility Review ^a	X	X							
Vital Signs ^b		X							
Demographics		X							
Medical History		X							
Concomitant Medications ^c		X			X				
Randomization		X							
Referral to HCV Treatment (SOC Arm Only)		X							
AE/SAE Collection ^d			→	→	→				
Laboratory Testing									
HBsAg		X							
Pregnancy Test ^e		X							
CBC ^f		X							
HCV RNA ^g		X			X	X		X	X
CMP		X			X	X			X
Urine Toxicology Screen		X			X	X	X	X	
Dried Blood Spot		X			X	X	X	X	X
Surveys/Questionnaires									
Study Survey		X			X	X	X	X	
PRO/QOL Measures		X			X	X	X	X	
Intervention Arm Only									
Peer Contact ^h		X	→	→	→	→			X
Study Drug Dispensation ⁱ			X	X					

^aIncluding documentation of HCV infection (antibody) and treatment history.

^bIncluding height, weight, temperature, pulse, respiratory rate, and blood pressure.

^cAll medication (including supplements and over-the-counter) will be collected.

^dAE/SAE collection starts with initiation of DAAs, continues through 30 days after last DAA dose.

^eFor all participants of childbearing potential. Urine or serum test.

^fWith or without differential.

^gCLIA certified.

^hPeer contact to occur weekly and as needed between visits until SVR 12. Contact can be in-person, via phone, or video.

ⁱStudy drug can be dispensed in smaller amounts more frequently if participant is unable to maintain 4-week supply at home.

APPENDIX B. SCHEDULE OF EVENTS (PARTICIPANTS WHO DO NOT START HCV TREATMENT BY WEEK 12 AFTER RANDOMIZATION IN EITHER ARM)

For participants who have not initiated treatment by Week 12 after randomization, complete the following.

	Week 12 after randomization -14d/+30d	Week 24 after randomization -14d/+30d	Week 36 after randomization -14d/+30d	Week 56 after randomization -14d/+30d
Laboratory Testing				
Urine Toxicology Screen	X	X	X	X
Dried Blood Spot	X	X	X	X
HCV RNA ^e		X		X
Surveys/Questionnaires				
Study Survey	X	X	X	X
PRO/QOL Measures	X	X	X	X
Rescreen for SOC Participants to Rollover to Intervention Arm				
Eligibility Review		X		
Vital Signs ^a		X		
Concomitant Medications ^b		X		
HBsAg		X		
Pregnancy Test ^c		X		
CBC ^d		X		
CMP		X		
Peer Contact ^f		→		

^aIncluding height, weight, temperature, pulse, respiratory rate, and blood pressure.

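### The SVR12 window closes at 36 weeks after treatment, but the Week 36 HCV RNA visit may run to 40.3 weeks, so some on-schedule results cannot count

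*Combined protocol and SAP*

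**What the plan says.** Section 3.3 gives the second secondary endpoint as "SVR 12: Proportion of participants with HCV RNA <15 IU/ml between 10 and 36 weeks after end of treatment in each randomization arm". Section 7.3.3 repeats the definition and adds "Analysis for secondary outcomes 1 and 2 will be logistic regression analyses".

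The HCV RNA results come from two schedules.

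- Appendix A, headed as applying to all participants, draws HCV RNA after treatment at the end-of-treatment visit, at "Post-Treatment Week 12 -14d/+30d" and at "Post-Treatment Week 36 -14d/+30d", plus an early-discontinuation visit. It draws none at post-treatment Week 24.
- Appendix B opens with "For participants who have not initiated treatment by Week 12 after randomization, complete the following". Its HCV RNA draws are at Week 24 and at "Week 56 after randomization -14d/+30d".

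On course length, the Synopsis says "Subjects will receive GLE/PIB fixed-dose combination (300 mg/120 mg) QD for 8 weeks". Section 6.2.2 allows that referred participants may have another regimen ("prescribed DAA course in SOC arm will be collected"), with no length given.

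The plan does not say which result decides if two fall in the window, or how a result drawn after 36 weeks is handled.

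**The concern.** The two ends of the endpoint window follow different rules. One carries the visit allowance and the other does not. A participant who missed the Week 12 draw, attends Week 36 within the permitted days and has undetectable HCV RNA can therefore supply a valid result that the definition excludes.

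For participants who start after week 12, the schedule appears to leave a single usable draw. Its distance from the end of treatment depends on the start date, and for the earliest of these starts it too can overrun the limit. SVR12 is compared by randomized arm. The plan assumes 40% uptake under referral against 70% under test and treat (section 7.3.1) and offers referral-arm non-starters treatment at 24 weeks (section 4.2.9). Late starts, and with them single and later samples, would probably be more common in the referral arm.

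**Working it through.** **Inputs.** Endpoint window 10 to 36 weeks after end of treatment (3.3, 7.3.3). Visit allowance -14/+30 days (Appendices A and B). Course length 8 weeks (Synopsis). Start time s, in weeks after randomization.

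**Step 1: reproduce the plan's limits.**

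- Lower: 12 weeks - 14 days = 84 - 14 = 70 days = 10.0 weeks. This matches the stated 10.
- Upper: 36 weeks + 30 days = 252 + 30 = 282 days = 40.3 weeks. This does not match the stated 36, which is the nominal visit date.

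**Step 2: Appendix A visits against the window.**

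- Week 12 visit: 10.0 to (84 + 30)/7 = 16.3 weeks, wholly inside.
- Week 36 visit: (252 - 14)/7 = 34.0 to 40.3 weeks. It can run 4.3 weeks past the limit, and 30 of its 44 window days (68%) lie after week 36.

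**Step 3: Appendix B visits, 8-week course begun at week s.** Treatment ends at s + 8.

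- Week 24 visit: latest permitted date 28.3, so at most 28.3 - 8 - s = 20.3 - s weeks after treatment. At s = 12 this is 8.3 weeks, below 10, so it never qualifies.
- Week 56 visit: permitted dates 54.0 to 60.3, so 46 - s at the earliest, 48 - s nominally and 52.3 - s at the latest.

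| Start week | Earliest | Nominal | Latest (weeks after treatment) |
|---|---|---|---|
| 12 | 34.0 | 36 | 40.3 |
| 16 | 30.0 | 32 | 36.3 |
| 24 | 22.0 | 24 | 28.3 |
| 32 | 14.0 | 16 | 20.3 |
| 36 | 10.0 | 12 | 16.3 |
| 42 | 4.0 | 6 | 10.3 |

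- The latest permitted draw exceeds 36 weeks when 52.3 - s > 36, that is, s < 16.3.
- The earliest permitted draw precedes 10 weeks when s > 36.
- No permitted draw qualifies when 52.3 - s < 10, that is, s > 42.3.

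**Step 4: a longer course in the referral arm.** Assuming 12 weeks, a length the documents do not give, the nominal Week 56 time is 44 - s. The latest permitted draw passes 36 weeks only for s < 12.3. The Week 24 draw is at most 28.3 - 12 - 12 = 4.3 weeks after treatment. There is still one qualifying draw.

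**Step 5: effect of extending the limit to 40.3 weeks.** Every in-window post-treatment Week 36 draw then counts. So does every in-window Week 56 draw after an 8-week course begun at weeks 12 to 36.

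**The case against.** The strongest reply is that little is lost. The Week 12 visit is the main source of SVR12 for early starters and lies wholly inside the window. A loss there needs both a missed Week 12 draw and a Week 36 visit after its nominal date. The 68% is a share of calendar days, not of participants. All of this stands.

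It can also be said that late starters are not confined to Appendix B. Appendix A is headed for all participants, its visits are tied to treatment, and Appendix B continues peer contact for rollovers until SVR12. Section 4.2.9 has staff collect care progress from the referral site, and the endpoint is not restricted to scheduled study draws. If late starters also had the post-treatment Week 12 visit, the late-starter part of this point would fall away. Against that, 12 + 8 + 36 = 56, so the Week 56 visit fits a replacement for post-treatment Week 36. The Version 3.0 entry in the change log also points to Appendix B only. The current text settles it neither way, so the finding is conditional.

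A reader might infer two stronger things.

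- **That excluded cures are scored as failures.** Neither 3.3 nor 7.3.3 says how a missing or out-of-window result is scored, and section 7.3.4 treats incomplete follow-up as missing data.
- **That later sampling exposes the referral arm to more reinfection and biases the cure comparison by a known amount.** The documents give no reinfection rate. At an assumed 5 to 20 per 100 person-years, 20 extra weeks gives 1 - exp(-r × 20/52) = 1.9% to 7.4% of cured late starters. But 20 extra weeks means a draw at 32 rather than 12 weeks, hence a start near week 16. Rollovers cannot start before about week 24, so their draw falls at about 24 weeks or less. Starts at weeks 32 to 38 are drawn at a nominal 10 to 16 weeks, like early starters.

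**Conclusion.** The mismatch is real and can be checked from the text. As written, the endpoint discards HCV RNA results that the visit schedule permits, for up to 4.3 weeks. For early starters the only loss is the back-up to a missed Week 12 draw. For starts at weeks 12 to 16.3 the loss can be the sole scheduled qualifying draw, provided that Appendix B alone applies and the course is 8 weeks. The absence of a rule for two in-window results is a related gap.

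Any imbalance would probably fall more on the referral arm, but its size is not established. That would need the distribution of start dates, attendance at Week 12 and a reinfection rate, none of which the documents supply. The primary endpoint (initiation within 12 weeks) and the sample size are unaffected. Severity: minor, on a secondary endpoint that carries the cure half of the clinical hypothesis in section 2.2.

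**What to change.** In sections 3.3 and 7.3.3:

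1. Extend the upper limit to the end of the visit allowance: 36 weeks + 30 days, about 40.3 weeks after end of treatment.
2. Define SVR12 by the first HCV RNA taken 10 or more weeks after end of treatment within that window.
3. Report a later positive after a qualifying negative separately, as recurrence.

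Reconcile Appendices A and B so that the text states which HCV RNA schedule applies to participants who start after week 12. This also settles what happens to very late starts, since under Appendix B alone the wider limit does nothing for starts after week 42.3.

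The cost is wording. The endpoint change needs no new visit or assay. The window becomes about 4 weeks wider, and sampling times will still differ between early and late starters. The change also cannot remove reinfection that occurs before a late starter's only sample. Report the time from end of treatment to the SVR12 sample by arm so that readers can judge this. A sensitivity analysis limited to samples at 10 to 16 weeks is not a good substitute: under Appendix B alone it would drop most late starters, and so probably exclude more of the referral arm.

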3.4 Exploratory Endpoints

- 1) Impact of test and treat versus standard of care referral on proportion of participants with change in substance use assessed by self-reported drug use in the preceding 30 days and urine toxicology at recruitment screening, end of HCV treatment, and post-treatment weeks 12, 24, and 36. Participants who do not start HCV treatment will be assessed at weeks 12, 24, and 36 post-randomization.
- 2) Impact of test and treat versus standard of care referral on subsequent substance use disorder treatment engagement-Proportion of expected weekly OTP visits actually attended, based on participant's OTP treatment plan.
- 3) Proportion of patients in the standard of care arm who are not offered treatment within 6 months (24 weeks) of randomization.
- 4) Proportion of patients in the standard of care arm who do not initiate treatment within 6 months (24 weeks) of randomization and subsequently initiate HCV treatment after study cross over to intervention arm.
- 5) Patient reported outcomes, quality of life measures, and patient satisfaction with test and treat model versus standard of care referral will also be assessed.
- 6) Proportion of participants with grade 3 or greater adverse events (AEs) in test and treat model versus standard of care referral.

4 INVESTIGATIONAL PLAN

[figure not shown]
4.1 Overall Study Design and Plan

This is an open label, multicenter, phase IV randomized trial to assess the effectiveness of an HCV test and treat strategy with peer enhancement compared to standard of care referral.

The study is designed to enroll approximately 124 HCV infected subjects at 4 drug treatment program sites in the US and 1 drug treatment program site in Canada.

We will also characterize the processes of implementation of peer supported on site HCV treatment at the drug treatment clinics including adoption, fidelity, drug treatment clinic staff acceptability, and drug treatment clinic workflow integration and congruence.

Figure 2: Study Schema

* Study laboratory testing (HCV RNA, CBC, CMP, HBsAg, BHcG) may be collected prior to randomization.

Test and treat strategy with peer support: Consistent with the approach in substance use self-help groups such as narcotics anonymous, the intervention will include support for HCV treatment initiation and completion from true peers (PWUD who have previously engaged in HCV treatment).

Peer Mentor selection and training: Many OTPs utilize peers as an element of substance use recovery. Each site will identify individuals with a history of drug use who have been treated for HCV and demonstrate good communication and interpersonal skills to serve as peers. These individuals may be referred to study staff by OTP staff. They will then be offered participation in the study and be consented to participate in the study as peers, and will undergo a tailored validated training (up to 5 hours) developed and successfully utilized in the CHAMPS trial¹⁵. Trainings will include in-depth discussions of HCV, HCV treatment and prevention of reinfection and skill development such as effective mentoring, active listening skills, facilitation, the importance of confidentiality, and harm reduction including overdose prevention. These trainings are divided into 5 modules which can be watched independently by peers. Modules are designed to be engaging with activities which the peer will complete during the module and then discuss with site research assistants during check-in sessions. Peers will be assessed to ensure they have mastered required competencies to function effectively as a peer prior to being permitted to serve in this role.

In the event a peer drops out, sites will be asked to identify other peers who have successfully completed HCV treatment who are interested in participating in the study as a peer. They will then go through the training process and undergo evaluation to ensure that they have mastered the required

competencies prior to being permitted to serve as peer.

The peers will meet and engage with participants in the test and treat strategy at the time of randomization, throughout treatment, and up to assessment of SVR 12. The key role of the peers will be to provide information, enhance motivation, and role model behavioral skills required for HCV treatment initiation, completion, and reinfection prevention.

Standard of care referral: Referral to off-site partner site with provision of clinic information for scheduling.

